**Table 9-1 Score Assignment for Body Region based on Body Surface Area (BSA) (Surface Area Involvement Score)**

Score to Assign	Percent of Body Region Involvement
0	No involvement
1	1% to 9%
2	10% to 29%
3	30% to 49%
4	50% to 69%
5	70% to 89%
6	90% to 100%

AGN-242428

### 9.1.2.2. Erythema, Thickness and Scaling Intensity Grading

**Erythema:** Each of the 4 body regions is given an erythema score ranging from 0 to 4:

- 0 = none
- 1 = slight
- 2 = moderate
- 3 = marked
- 4 = very marked

**Thickness (induration):** Each of the 4 body regions is given an induration score ranging from 0 to 4:

- 0 = none
- 1 = slight
- 2 = moderate
- 3 = marked
- 4 = very marked

**Scaling (desquamation):** Each of the 4 body regions is given a scaling score ranging from 0 to 4:

- 0 = none
- 1 = slight
- 2 = moderate
- 3 = marked
- 4 = very marked

### 9.1.2.3. Calculate the PASI score

**Body region score:** First sum the intensity grading for erythema, thickness and scaling for each of the body regions. The intensity score for each body region will fall within the range of 0 to 12 (see Section 9.1.2.2). Next multiply the intensity body region score by the surface area involvement score. The surface area involvement score will fall within the range of 0 to 6 (see Section 9.1.2.1). Finally, multiply by the total % of BSA accounted for by each body region and this will be the body region score.

Individual intensity and surface area involvement scores will be recorded for each body region. The eCRF will calculate the body region and total PASI scores. The total PASI score will fall within the range of 0 to 72. A PASI calculator is provided below.

AGN-242428

**Table 9-2 Psoriasis Area and Severity Index (PASI) calculator**

Body Regions	
Head and Neck	$(E + T + Sc) \times \text{surface area involvement score} \times 0.1$
Body Region Score	$(\_ + \_ + \_) \times \underline{\hspace{2cm}} \times \underline{\hspace{2cm}}$
Upper Extremities	$(E + T + Sc) \times \text{surface area involvement score} \times 0.2$
Body Region Score	$(\_ + \_ + \_) \times \underline{\hspace{2cm}} \times \underline{\hspace{2cm}}$
Trunk (includes axillae and groin)	$(E + T + Sc) \times \text{surface area involvement score} \times 0.3$
Body Region Score	$(\_ + \_ + \_) \times \underline{\hspace{2cm}} \times \underline{\hspace{2cm}}$
Lower Extremities (includes buttocks)	$(E + T + Sc) \times \text{surface area involvement score} \times 0.4$
Body Region Score	$(\_ + \_ + \_) \times \underline{\hspace{2cm}} \times \underline{\hspace{2cm}}$
PASI =	Head and neck + Upper extremities + Trunk + Lower extremities $\underline{\hspace{2cm}} + \underline{\hspace{2cm}} + \underline{\hspace{2cm}} + \underline{\hspace{2cm}}$

PASI = Psoriasis Area and Severity Index

E = erythema; T = thickness; Sc = scaling

### 9.1.3. Physician's Global Assessment

The PGA will be completed by the same trained and qualified dermatologist, to the extent possible, at all study timepoints when PGA is assessed, including the screening and baseline visits. The same trained and qualified dermatologist must determine the baseline and Week 16 PGA. A 5-point scale (0 to 4) will be used and is described in [Table 9-3](#).

AGN-242428

**Table 9-3** Physician's Global Assessment (PGA) Scoring

Score	Severity	Description
0	Clear	Plaque elevation = 0 (no elevation over normal skin); Scaling = 0 (no evidence of scaling); Erythema = 0 (except for residual hyperpigmentation /hypopigmentation)
1	Almost clear	Plaque elevation = $\pm$ (possible but difficult to ascertain whether there is a slight elevation above normal skin); Scaling = $\pm$ (surface dryness with some desquamation); Erythema = $\pm$ (fading, diffuse pink or slight red coloration)
2	Mild	Plaque elevation = slight (slight but definite elevation, typically edges are indistinct or sloped); Scaling = fine (fine scale partially or mostly covering lesions); Erythema = mild (light red coloration)
3	Moderate	Plaque elevation = marked (marked definite elevation with rough or sloped edges); Scaling = coarser (coarser scale covering most or all of the lesions); Erythema = moderate (definite red coloration).
4	Severe	Plaque elevation = marked (marked elevation typically with hard or sharp edges); Scaling = coarser (coarse, non-tenacious scale predominates covering most or all of the lesions); Erythema = severe (very bright red coloration)

For PGA scores recorded after initiation of treatment, the assessment of overall severity will include areas that have already been cleared (scores of 0) and will not be scored only on remaining lesions. The severity will be averaged across all areas of involvement including cleared lesions. When severities differ across the disease parameters evaluated (erythema, scaling and induration), the parameter that is the predominant feature of the disease should be used to determine the PGA score.

#### 9.1.4. Photograph of Primary Lesion

Photography of primary lesions will be taken in a subset of participants that consent to have their photos taken. A primary lesion that is representative of the severity of the PGA and PASI scores at baseline (Day 1) will be selected and photographed at scheduled visits (Section 2). The images can be captured before or after the study medication is administered. Conditions of photography will be standardized across all photos including camera equipment, exposure, background, lighting and focal length. Ideally, the same photographer will take all required photos.

A qualified third party vendor will provide instructions for taking photographs and processing digital photographs. Photographs will be transferred to sponsor on a periodic basis and all digital images will be transferred to sponsor at the end of the study. Participants will provide consent to

## AGN-242428

be photographed and by consenting to have photographs taken, participants are indicating their understanding that they give permission for use of their study photographs for general research, education or informational purposes. Participants may decline permission for use of their study photographs for advertising, publicity, and promotional purposes.

A series of 12 horizontal black bars of varying lengths, decreasing from left to right. The first bar is the longest, followed by a short bar, then a long bar, then a very long bar, then a short bar, then a long bar, then a very long bar, then a short bar, then a long bar, then a very long bar, then a short bar, and finally a long bar. The bars are set against a white background.

AGN-242428

[REDACTED]

## 9.2. Adverse Events

The definitions of an AE or SAE can be found in Appendix 3 (Section 12.3).

AEs will be reported by the participant (or, when appropriate, by a caregiver or surrogate).

The investigator and any designees are responsible for detecting, documenting, and recording events that meet the definition of an AE or SAE and any other study-specific terms as relevant and remain responsible for following up AEs that are serious, considered related to the study treatment or study procedures, or that caused the participant to discontinue the study treatment and/or study (see Section 8).

### 9.2.1. Time Period and Frequency for Collecting AE and SAE Information

All AEs (serious and non-serious) from the signing of the informed consent form (ICF) until the follow-up visit will be collected at the timepoints specified in the schedule of activities (Section 2), and as observed or reported spontaneously by study participants.

Medical occurrences that begin before the start of study treatment but after obtaining informed consent will be recorded on the AE section of the eCRF.

All SAEs will be recorded and reported to the sponsor or designee within 24 hours, as indicated in Appendix 3 (Section 12.3). The investigator will submit any updated SAE data to the sponsor within 24 hours of it being available.

Investigators are not obligated to actively seek AE or SAE information in former study participants. However, if the investigator learns of any SAE, including a death, at any time after a participant has been discharged from the study, and he/she considers the event to be reasonably related to the study treatment or study participation, the investigator must promptly notify the sponsor.

The method of recording, evaluating, and assessing causality of AEs and SAEs and the procedures for completing and transmitting SAE reports are provided in Appendix 3, Section 12.3.

### 9.2.2. Method of Detecting AEs and SAEs

Care will be taken not to introduce bias when detecting AEs and/or SAEs. Open-ended and non-leading verbal questioning of the participant is the preferred method to inquire about AE occurrences.

AGN-242428

### **9.2.3. Follow-up of AEs and SAEs**

After the initial AE/SAE report, the investigator is required to proactively follow each participant at subsequent visits/contacts. All AEs, SAEs, and adverse events of special interest (AESI), including out of reference range laboratory test results, will be followed until resolution, stabilization, until the event is otherwise explained, or the participant is lost to follow-up (as defined in Section 8.3).

The investigator is obligated to perform or arrange for the conduct of supplemental measurements and/or evaluations as medically indicated or as requested by the sponsor to elucidate the nature and/or causality of the AE or SAE as fully as possible. This may include additional laboratory tests or investigations, histopathological examinations, or consultation with other health care professionals.

If a participant dies during participation in the study or during a recognized follow-up period, the investigator will provide the sponsor with a copy of any postmortem findings including histopathology.

New or updated information will be recorded in the originally completed eCRF.

The investigator will submit any updated SAE data to the sponsor within 24 hours of receipt of the information.

### **9.2.4. Regulatory Reporting Requirements for SAEs**

Prompt notification by the investigator to the sponsor of a SAE is essential so that legal obligations and ethical responsibilities towards the safety of participants and the safety of a study treatment under clinical investigation are met.

The sponsor has a legal responsibility to notify both the local regulatory authority and other regulatory agencies about the safety of a study treatment under clinical investigation. The sponsor will comply with country-specific regulatory requirements relating to safety reporting to the regulatory authority, institutional review boards (IRBs)/independent ethics committees (IECs), and investigators.

Investigator safety reports must be prepared for suspected unexpected serious adverse reactions (SUSARs) according to local regulatory requirements and sponsor policy and forwarded to investigators as necessary.

An investigator who receives an investigator safety report describing a SAE or other specific safety information (eg, summary or listing of SAEs) from the sponsor will review and then file it, along with the IB, and will notify the IRB/IEC, if appropriate according to local requirements.

### **9.2.5. Cardiovascular and Death Events**

Not applicable.

AGN-242428

### **9.2.6. Disease-Related Events and/or Disease-Related Outcomes Not Qualifying as AEs or SAEs**

Progression of the treatment indication (ie, the disease under investigation), including new occurrence or worsening of anticipated clinical signs or symptoms collected as clinical efficacy variables and assessed as unequivocally associated with the disease progression and /or lack of efficacy, should NOT be reported as an adverse event unless the disease progression is greater than anticipated in the natural course of the disease.

### **9.2.7. Pregnancy**

Details of all pregnancies in female participants and, if indicated, female partners of male participants will be collected after the start of study treatment and until 30 days after the last dose.

If a pregnancy is reported, the investigator should inform the sponsor within 24 hours of learning of the pregnancy and should follow the procedures outlined in Appendix 4 (Section 12.4).

Abnormal pregnancy outcomes (eg, spontaneous abortion, elective termination of a pregnancy, fetal death, stillbirth, congenital anomalies, ectopic pregnancy) are considered SAEs (Appendix 3, Section 12.3).

### **9.2.8. Adverse Events of Special Interest**

All of the following are AESI:

- AST and/or ALT increased to  $\geq 5$  ULN
- AST and/or ALT increased to  $\geq 3 \times$  ULN AND TBL increased to  $\geq 2 \times$  ULN or INR  $> 1.5$ . Typically, all analytes will be obtained from the same sample, but they may come from multiple samples taken within a 24-hour period.
- AST and/or ALT increased to  $\geq 3 \times$  ULN with symptoms believed to be related to liver injury (eg, fatigue, nausea, vomiting, right upper quadrant pain or tenderness or jaundice) or hypersensitivity (such as fever, rash or eosinophilia  $> 5\%$ )
- For any participant who meets one of the above liver criteria resulting in study treatment discontinuation, the following must be performed (See Appendix 3, Section 12.3, for additional details regarding the reporting of AESIs):
  - 1) The lab abnormality captured as an AESI
  - 2) Non-serious AESIs should be reported to the sponsor within 72 hours and serious AESIs should be reported to the sponsor within 24 hours
  - 3) The AESI form, which is the Adverse Event of Interest Abnormal Liver Function Reporting Form, should be completed and used for reporting the AESI even if a serious outcome may not apply, and

AGN-242428

4) Every effort to determine the cause of the liver enzyme abnormalities must be made (in conjunction with the MSP and in accordance with the [FDA Guidance for Industry, Drug-Induced Liver Injury: Premarketing Clinical Evaluation, July 2009](#)).

In addition, a potential Hy's Law case is also an AESI. Criteria for potential Hy's Law cases are as follows:

- ALT and/or AST  $\geq 3 \times$  ULN AND
- TBL  $\geq 2 \times$  ULN AND
- Alkaline phosphatase  $< 2 \times$  ULN

Study site personnel must report every participant who meets these potential criteria. Typically, all 3 analytes will be obtained from the same sample, but they may come from multiple samples taken within a 24-hour period. This requirement applies from the time the participant signs the ICF for the study until 30 days after the final protocol-defined study visit or the last known dose of study treatment (if the final visit does not occur).

A laboratory alert for potential Hy's Law cases will be in place, and must notify investigators and the sponsor immediately when the above criteria have been met. A potential Hy's law case must be reported as a SAE by completing an Adverse Event of Interest Abnormal Liver Function Reporting Form and sent to [[contact]](mailto:[contact]) (or faxed to the SAE fax number) as soon as possible (within 24 hours of learning of the potential Hy's Law case). The eCRF for potential Hy's Law cases must be completed within 7 calendar days. Every effort to determine the cause of the liver enzyme abnormalities must be made, and close monitoring should be initiated in conjunction with the MSP and in accordance with the [FDA Guidance for Industry, Drug-Induced Liver Injury: Premarketing Clinical Evaluation, July 2009](#).

Suggested actions and follow-up assessments for liver safety are described in Appendix 6 (Section 12.6).

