c Discontinuation of study treatment for abnormal liver function should be considered by the investigator when a participant meets one of the conditions outlined, or if the investigator believes that it is in best interest of the participant.

Liver Safety Suggested Actions and Follow-up Assessments Section can be found in Appendix 6, Section [12.6](#).

See the SoA (Section [2](#)) for data to be collected at the time of treatment discontinuation and follow-up and for any further evaluations that need to be completed.

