## 12.3. Appendix 3: Adverse Events: Definitions and Procedures for Recording, Evaluating, Follow-up, and Reporting

### Definition of AE

AE Definition

An AE is any untoward medical occurrence in a participant or clinical study participant, temporally associated with the use of study treatment, whether or not considered related to the study treatment.
 
NOTE: An AE can therefore be any unfavorable and unintended sign (including an abnormal laboratory finding), symptom, or disease (new or exacerbated) temporally associated with the use of study treatment.
 
AE of Special Interest (AESI)
 
An adverse event of special interest (serious or nonserious) is one of scientific and medical concern specific to the sponsor's study treatment/device or program, which warrants ongoing monitoring and rapid communication by the investigator to the sponsor. Such an event might warrant further investigation in order to characterize and understand it.
 
The following AESI(s) have been identified for the study treatment(s) in this protocol:
 

• AST and/or ALT <math>\geq</math> 5 ULN

• AST and/or ALT <math>\geq</math> 3 x ULN AND TBL <math>\geq</math> 2 x ULN or INR <math>></math> 1.5. Typically, all analytes will be obtained from the same sample, but they may come from multiple samples taken within a 24-hour period.

• AST and/or ALT <math>\geq</math> 3 x ULN with symptoms believed to be related to liver injury (eg, fatigue, nausea, vomiting, right upper quadrant pain or tenderness or jaundice) or hypersensitivity (such as fever, rash or eosinophilia <math>></math> 5%)

• Changes in hepatic laboratory test results that meet potential Hy's Law

• ALT and/or AST <math>\geq</math> 3 x ULN AND

• TBL <math>\geq</math> 2 x ULN AND

• Alkaline phosphatase <math><</math> 2 x ULN

 
Typically, all 3 analytes will be obtained from the same sample, but they may come from multiple samples taken within a 24-hour period. Non-serious AESIs should be reported to the sponsor within 72 hours and serious AESIs should be reported to the sponsor within 24 hours. The AESI form, which is the Adverse Event of Interest Abnormal Liver Function Reporting Form, should be used for reporting the AESI even if a serious outcome may not apply. Of note, all potential Hy's Law cases are to be reported as SAEs.

AGN-242428

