11.1.1 Adverse Events of Special Interest

The following adverse events of special interest (AESI) will be summarized by treatment group:

- aspartate aminotransferase (AST) and/or alanine aminotransferase (ALT) $\geq 5 \times$ upper limit of normal (ULN)
- AST and/or ALT $\geq 3 \times$ ULN AND total bilirubin (TBL) $\geq 2 \times$ ULN or international normalized ratio (INR) > 1.5
- AST and/or ALT $\geq 3 \times$ ULN with symptoms believed to be related to liver injury (eg, fatigue, nausea, vomiting, right upper quadrant pain or tenderness or jaundice) or hypersensitivity (such as fever, rash, or eosinophilia $> 5\%$)
- Changes in hepatic laboratory test results that meet potential Hy's Law
 - ALT and/or AST $\geq 3 \times$ ULN AND
 - TBL $\geq 2 \times$ ULN AND
 - Alkaline phosphatase $< 2 \times$ ULN

Potential Hy's Law criteria within a 24-hour window is defined by a postbaseline elevation of ALT and/or AST $\geq 3 \times$ ULN, along with TBL $\geq 2 \times$ ULN and a non-elevated alkaline phosphatase (ALP) $< 2 \times$ ULN, all based on blood draws collected within a 24-hour period.

A graphical representation of liver function, known as eDISH, will be generated by plotting the maximum postbaseline TBL elevation at any timepoint during the study vs maximum postbaseline ALT elevation at any timepoint. Note that the maximum ALT may be from a different visit than when the maximum TBL was observed. A plot of maximum TBL vs maximum AST will be generated separately.

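### Protocol 9.2.8 ties AESI recording of three liver criteria to stopping treatment, while Appendix 3 and SAP 11.1.1 do not, so sites may record these events inconsistently

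*Protocol*

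**What the plan says.** Protocol 9.2.8 opens its list of liver criteria with "All of the following are AESI". Three criteria follow:

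1. AST and/or ALT at or above 5 x ULN.
2. AST and/or ALT at or above 3 x ULN together with total bilirubin at or above 2 x ULN or INR above 1.5.
3. AST and/or ALT at or above 3 x ULN with symptoms of liver injury or hypersensitivity.

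The next item in the same list reads "For any participant who meets one of the above liver criteria resulting in study treatment discontinuation, the following must be performed". Four duties hang on it: "The lab abnormality captured as an AESI", reporting within 72 hours (24 hours if serious), completion of the liver AESI form, and a search for the cause.

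Potential Hy's Law is a fourth AESI with its own rule: "Study site personnel must report every participant who meets these potential criteria". That rule runs from consent "until 30 days after the final protocol-defined study visit or the last known dose of study treatment".

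Appendix 3 (Section 12.3), to which the conditional sentence refers, lists the same four criteria, names the same form and says: "Non-serious AESIs should be reported to the sponsor within 72 hours and serious AESIs should be reported to the sponsor within 24 hours". It does not mention discontinuation. SAP 11.1.1 repeats the four criteria under "The following adverse events of special interest (AESI) will be summarized by treatment group", again without that condition.

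**The concern.** A definition that covers every case and a recording duty that covers only some cannot both govern the same count. The SAP's by-arm table is meant to show how many participants met each criterion. If recording follows the stopping decision, the table partly shows how often investigators stopped treatment.

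This matters more than a routine wording slip because the liver is the known safety question for this drug. Protocol 5.5 reports transaminase elevations at one dose level of the earlier proof-of-concept trial and not at another, so a comparison of liver events across arms is a main safety output. The Hy's Law paragraph also sits directly after the conditional sentence and says explicitly that it covers everyone. A site reading the two together could reasonably take the narrower wording for the other three criteria as deliberate.

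**Working it through.** No figure in the plan bears on this point, so the check sets the texts side by side.

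**Step 1. Which criteria carry the condition?**

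| Criterion | Protocol 9.2.8 duties | Appendix 3 | SAP 11.1.1 | Can it be rebuilt from laboratory data? |
|---|---|---|---|---|
| 1. Transaminases at or above 5 x ULN | only if treatment stops as a result | no condition | no condition | yes |
| 2. At or above 3 x ULN with raised bilirubin or INR | only if treatment stops as a result | no condition | no condition | yes |
| 3. At or above 3 x ULN with symptoms | only if treatment stops as a result | no condition | no condition | not fully; attribution of symptoms is a judgement |
| 4. Potential Hy's Law | every participant | no condition | no condition | yes; the SAP defines it from blood draws |

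The count of conditional criteria is 3 of 4 under 9.2.8, 0 of 4 under Appendix 3 and 0 of 4 in the SAP. Of the 3, laboratory values recover 2, which leaves 1.

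**Step 2. Can a criterion be met without treatment stopping?** Protocol 8.1 requires withdrawal when a Table 8-1 criterion is met and considered related to the drug, so an event judged unrelated need not lead to stopping. Footnote c to Table 8-1 says "Discontinuation of study treatment for abnormal liver function should be considered by the investigator when a participant meets one of the conditions outlined", which leaves room to continue. Footnote a asks for a confirmatory repeat within 2 to 5 days for criteria 1 and 3, whereas the AESI definition asks for none. Appendix 6 says the opposite: its liver stopping criteria include the same three, and its action is immediate, permanent discontinuation with no relatedness test. The protocol therefore conflicts with itself on whether such participants continue.

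**Step 3. Can a criterion be met after treatment has ended?** Yes, and this does not depend on Step 2. The follow-up visit is 14 ± 3 days after the last dose. A criterion first found there cannot result in discontinuation, because there is nothing left to discontinue. The same applies after early withdrawal for another reason. A Week 16 result may also fall here: that visit's dose is given on site (7.1.1, 7.6) and tests go to the central laboratory (9.4.4), so the result would be expected after the last planned dose. The schedule of activities is redacted, so it is an assumption that liver chemistry is drawn at follow-up. Section 9.4.4 does provide for repeating abnormal values up to 30 days after the last dose.

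**Step 4. Does the SAP settle the source?** No. SAP 11.1.1 gives a blood-draw definition for potential Hy's Law only. For criteria 1 to 3 it does not say whether the count comes from the AESI form or the laboratory data, and it gives no time window. SAP 16.2 on derived variables says not applicable.

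**The case against.** The case against is substantial, and most of it stands.

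- Appendix 3 imposes the AESI timelines and form without condition, and 9.2.8 points to it. A site that follows the cross-reference would record every case.
- Appendix 6 separately requires sponsor notification within 24 hours, a liver event eCRF and recording of liver or hypersensitivity symptoms for the same three criteria. It also requires 24-hour notification for asymptomatic ALT from 3 to below 5 x ULN (with bilirubin below 2 x ULN) when treatment continues.
- All AEs are collected from consent to follow-up (9.2.1), and clinically relevant laboratory changes go on the AE page (9.4.4).
- The SAP's eDISH plots use maximum postbaseline values, and its listings flag ALT or AST at or above 3 x ULN and INR above 1.5, whatever is on an AESI form.
- There is a benign reading: since Appendix 6 treats the three as stopping criteria, the qualifier may only describe them.

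A reader might therefore infer too much from 9.2.8 in three ways. One is that these events escape the safety data, or that the symptom criterion is captured only in those who stopped. The provisions above do not support that. Another is that the sponsor is not notified, which Appendix 6 contradicts. The third is that the loss can be sized from the time between the last scheduled visits. That would need a constant hazard and no unscheduled draws, and would give the share of events first seen late, not the share lost.

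The benign reading does not remove the defect. It fails for events found after dosing, and 8.1 with footnote c allows continuation. What may be missing is the AESI entry, its form and, for criterion 3, the investigator's attribution of symptoms to the liver.

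**Conclusion.** The inconsistency is real and its reach is limited. For three of four liver AESIs, 9.2.8 makes capture and reporting depend on discontinuation, contrary to its own opening line, Appendix 3 and the SAP. Such events may be missed as AESIs or recorded differently from site to site, across approximately 40 centres. The practical exposure is mainly the symptom criterion.

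No number of affected events can be given: the documents state no expected liver event rate, and the schedule is redacted. The conclusion for participants who continue rests on 8.1 and footnote c being applied instead of Appendix 6. The conclusion for events after dosing does not depend on that conflict, but assumes that liver chemistry is drawn once dosing has ended. The point is worth correcting because the liver is the known signal and the correction is cheap. It does not undermine the laboratory-based liver safety analyses.

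**What to change.** 1. In Protocol 9.2.8, for capture and reporting, remove the words that make the duties depend on treatment being discontinued. The AESI entry, timed report and liver form would then apply to every participant who meets a listed criterion through the follow-up visit, as the opening line and Appendix 3 already imply. Leave stopping and work-up decisions to the clinical sections.
2. In SAP 11.1.1, state that criteria 1 and 2 and potential Hy's Law are counted from laboratory data and the symptom criterion from the AESI form, and give the time window for each.
3. Reconcile 8.1 and Table 8-1 footnote c with Appendix 6 on what follows when a liver criterion is met, and reconcile the 72-hour limit for non-serious AESIs with the 24-hour limit in Appendix 6. No view is taken here on which clinical rule should prevail.

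Item 1 is one phrase in an amendment or site letter, and item 2 is one or two sentences. Item 3 needs a decision by the sponsor's clinical team. The downside of items 1 and 2 is a few more liver forms.
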